3. CHARACTERISTICS OF THE RESEARCH POPULATION

3.1: Subject Characteristics

a. Number of Subjects: It is anticipated that this study will enroll a total of approximately 180 subjects. This includes 60 children between the ages of 24 and 35 months in the first cohort. These children will be divided equally into two groups of 30, with one group receiving IIV and the other receiving LAIV as described above. We expect to screen up to 120 subjects into the second cohort, of whom 45 will be enrolled in the full study and evaluable. This will include 30 children between the ages of 6 months and 1 year that will receive IIV and 15 children between the ages of 3 months and 1 year who become naturally infected with influenza virus. However, in order to enroll these 15 naturally infected children, we anticipate having to screen up to 90 children with signs of influenza like illness during the height of seasonal influenza circulation, as only a small number of these children will have respiratory infections as a result of influenza virus infection.

b. Gender and Age of Subjects: It is anticipated that there will be an approximately equal distribution of males and females enrolled. This will include 60 children between the ages of 24 and 35 months in the first cohort and up to 120 children between the ages of 3 months and 1 year in the second cohort, of whom 45 will be evaluable.

c. Racial and Ethnic Origin: It is anticipated that the demographic distribution of enrollment will approximately resemble that of the City of Rochester, which is about 40% Caucasian, 40% African-American, 15% Hispanic, and 5% other. No subject will be excluded because of their racial or ethnic origin.

d. Vulnerable Subjects: As the goal of this study is the study of the early immune response to childhood influenza infection and vaccination, by definition it needs to include children, who are a vulnerable population. To safeguard rights and welfare of these children, the parents or legal guardians of all subjects recruited into this study will provide written informed consent. Since the subjects involved will all be less than 3 years of age, it will not be possible to obtain subject assent, although study procedures will be explained to all subjects as developmentally appropriate based on the subject's age. To maintain subject privacy, paper copies of subject PHI will be stored in a locked file cabinet within a locked office, with an electronic extraction of this data maintained on a password protected and secured university computer.

All blood will be drawn by experienced and trained pediatric nurses, with pain minimized through comforting and distraction techniques. Only the minimum amount of blood necessary to achieve the study objectives will be obtained, with the blood volume being within a level accepted as safe (Table 1). As a child's total blood volume is related to body weight, we have chosen a weight based approach to determine the volume of blood to be obtained. This will allow us to optimize our likelihood of being able to accomplish the study objectives while still prioritizing the safety of the child. Current policy suggests that blood volume limits between 1% and 5% of the total blood volume on a single draw and up to 10% of total blood volume over an 8 week period will present minimal risk to children (76). A child's total blood volume estimated at around 80 mL/kg. The proposed blood draws in this protocol impose a maximum upper limit of 1 mL/kg on any single draw (about 1.25% of estimated TBV), with a maximum of 3 mL/kg (about 3.75% of estimated TBV) over any 8 week period for all pediatric patients. This volume remains well below the upper limit of 10% of total blood volume in an 8 week period and is consistent with the available evidence on what will present minimal risk to children while still providing enough PBMCs to perform the in depth analysis of CD4 T cell specificity and functional capacity and antibody responses required for this study.

3.2: Inclusion and Exclusion Criteria

a. Inclusion Criteria:

- Age

- Between 24 and 35 months for cohort 1
- Between 6 and 12 months to participate in the vaccination arm of cohort 2 (cohort 2A)
- Between 3 and 12 months to participate in the natural infection arm of cohort 2 (cohort 2B)
- Gestational age of ≥ 37 weeks at birth
- Parent/guardian can provide informed consent
- Available for the duration of the study
- History of previous IIV administration **ONLY** for participation in cohort 1
- Acute illness documented to be due to influenza virus **ONLY** for participation in the natural infection arm of cohort 2 (cohort 2B)

b. Exclusion Criteria:

- Immunosuppression as a result of an underlying illness or condition (including HIV or a primary immunodeficiency syndrome)
- Active neoplastic disease
- Use of potentially immunosuppressive medications currently or within the past year (including chemotherapeutic agents) or chronic (>2 weeks) use of oral or inhaled steroid therapy
- A diagnosis of asthma requiring chronic controller medication
- Previous administration of influenza vaccine in the current influenza season
- Receipt of immunoglobulin or another blood product within the year prior to study enrollment
- An acute illness within the previous 3 days or temperature $>38^{\circ}$ on screening **EXCEPT** for participation in the natural infection arm of cohort 2 (cohort 2B)
- A contraindication to influenza vaccination **EXCEPT** infants between 3 and 5 months presenting with natural influenza infection whose only contraindication is their current age

3.3: Discussion of Subject Population:

The main objective of this Study is to evaluate the specificity and functional potential of the CD4 T cell response and the quantity, breadth and avidity of the neutralizing antibody response following influenza infection or vaccination. In order to eliminate potential confounding factors, we plan to exclude any subject who has an acute or chronic medical condition that may result in immunosuppression. Also excluded will be potential subjects that have recently received immunosuppressive medications or blood products that could potentially interfere with vaccine immunogenicity. This exclusion will include children with a history of asthma who require chronic controller medicines, including inhaled steroids. Children with only a history isolated wheezing not on chronic controller therapy will be allowed to participate, although they will not be administered LAIV.

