The age range of the first cohort of children was chosen because children first become eligible to receive LAIV at the age of 24 months. Thus, the age range of 24 through 35 months will capture children receiving LAIV for the first time. A block randomization scheme will be used as there is a large population of children with a past history of isolated wheezing as a result of viral illnesses such as bronchiolitis that have been shown to respond

equivalently to influenza vaccine (59, 74, 75). We feel that including this population of children in the study will improve recruitment and allow for broader applicability of our study results, but as these subjects are not eligible to receive LAIV (17, 18), their inclusion also precludes a completely blinded randomization scheme. With block randomization, eligible subjects will be enrolled to receive either LAIV or IIV in groups of 5 unless a history of isolated wheezing in the past year is present, in which case they will be defaulted to receive IIV as long as no other exclusion criteria are present.

The age range of the second cohort was chosen to enroll infants in their first influenza season with no history of prior exposure to influenza virus. Thus, this cohort will allow examination of the true primary response to influenza infection or inactivated vaccination. Children between 6 and 12 months of age who have not previously had an influenza infection or vaccination will be eligible to participate in the vaccination group. All of these children will receive IIV, as LAIV is not approved for children this age. This cohort will receive a prime-boost vaccination series, with vaccine doses separated by 28 (+ 14) days as recommended by the AAP and ACIP (17, 18). To minimize blood draws, we will only interrogate the immune response following the second vaccine dose. Children between 3 and 12 months of age who present with an influenza-like illness and have no previous history of influenza vaccination will be eligible to participate in the infection group. Study personnel will obtain nasal swabs from potential subjects for a rapid influenza antigen test on illness presentation (typically this occurs at day 3-4 post illness onset). If positive, they will be eligible for further study participation. Influenza real-time RT-PCR will be used to confirm rapid antigen test results, however these results will not be available in time to influence subject enrollment.

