8. STUDY DRUG/DEVICE/BIOLOGIC ADMINISTRATION/ASSIGNMENT

8.1: Study Drug/Device/Biologic:

Influenza vaccines will be administered using age-appropriate guidelines in years 1 and 2 of the study. In year 2, all subjects will be administered IIV during a fall study visit in the VRU.

- Live vaccine will consist of Flumist Quadrivalent (MedImmune Vaccine), supplied in a pre-filled, single-dose intranasal sprayer. Each 0.2 mL dose contains $10^{6.5-7.5}$ fluorescent focus units of live attenuated influenza virus reassortants of each of the 4 strains (A/H1N1, A/H3N2, B/Yamagata and B/Victoria). Each dose is formulated in a sucrose phosphate buffer and may contain residual amounts of ovalbumin, gentamicin, and EDTA. Flumist contains no preservatives.
- Inactivated vaccine will consist of Fluzone Trivalent or Quadrivalent vaccine. This vaccine is approved for use in persons 6 month of age and older. It consists of a split and chemically inactivated influenza virus and is formulated to contain 7.5 mcg of each HA protein per 0.25 mL vaccine in sodium phosphate-buffered isotonic sodium chloride solution. This vaccine also may contain 12.5 mcg of thimerosal and trace amounts of formaldehyde in each 0.25 mL dose.

8.2: Dosage of Study Drug/Biologic

All influenza vaccines will be administered at the recommended doses for age:

- LAIV: Flumist Quadrivalent (MedImmune) 0.2 mL administered intranasally
- IIV: Fluzone 0.25 mL administered intramuscularly to children between 6 and 35 months of age
 - Children in cohort 2 (6-12 months of age) who are receiving influenza vaccine for the first time will receive 2 doses separated by 28 days +14 days

8.3: Study Enrollment/Randomization:

We plan to enroll a cohort of 60 children who have previously been vaccinated with at least 2 doses of IIV and who are between the ages of 24 and 35 months into vaccination cohort 1. These children will be block randomized to receive either LAIV (n=30) or IIV (n=30) in groups of 5 unless a history of isolated wheezing in the past year is present. As LAIV is not indicated in children with a history of recent wheezing, eligible children who give a history of isolated wheezing will be defaulted to receive IIV.

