13. DATA ANALYSIS AND MONITORING

13.1: Sample Size Determination:

	d=0.3	d=0.35	d=0.4
n1=25, n2=25	0.738	0.858	0.934
n1=30, n2=30	0.815	0.915	0.968
n1=35, n2=35	0.871	0.95	0.985
n1=30, n2=10	0.517	0.646	0.761
n1=30, n2=15	0.64	0.772	0.871
n1=30, n2=20	0.721	0.844	0.924

The primary endpoint of this study is CD4 T cell responses. Based on a study of immune response in children and adults (62), the overall mean percentage of IFN γ + CD4 T cells in 5-9 year old children vaccinated with IIV or LAIV is around 0.1%, or -3 in log₁₀ scale. The standard deviation (STD) in log₁₀ scale is around 0.4. The geometric mean differences induced by vaccinations or between the two types of vaccination is around 0.3 in log₁₀ scale. The above table summarizes statistical power based on Student's two sample *t*-test. Assuming our responses are similar, recruiting n=30 subjects in each group will give us adequate power (0.815) for Aim 1. Because LAIV is an attenuated virus, it is reasonable to assume that the difference in CD4 T cell responses induced by IIV and natural influenza infection is larger (d=0.4), therefore recruiting

n=30 subjects in the IIV group and n=15 subjects in the infection group can achieve adequate power (0.871) for Aim 2. For Aim 3, assuming that within-group STD is 0.4 and between-group STD is just 0.2, the power is 0.851 if we recruit n=105 subjects divided them into four subgroups (n1=30, n2=30, n3=30, n4=15).

13.2: Planned Statistical Analysis:

We outline the statistical analysis strategies for the specific aims as follows. **Aim 1:** A cohort of n=60 healthy children will be recruited and divided into two groups with equal sample size (n=30); one group will be vaccinated with LAIV and the other with IIV. Their T cell and antibody responses will be measured at three time points: Baseline, day 10, and day 24 post-vaccination. We will apply Shapiro-Wilk's test to check the normality. If the data passes the normality test, two sample *t*-tests will be used to detect significant mean difference between the two groups at each time point. Otherwise, Wilcoxon rank-sum test will be used. Because multiple response variables are used in this analysis, the *p*-values will be adjusted by the Benjamini-Hochberg multiple testing procedure (80) to control the false discovery rate (FDR) at the level of 0.05. In addition to pairwise comparisons, the following linear mixed effect model will be used to analyze data collected from all time points:

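### Cohort 1 fixes the arms at 30 LAIV and 30 IIV but counts non-randomised wheezing children in the IIV arm, so the LAIV-eligible children cannot end up split 1:1, and no fill rule says how they are allocated

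*Combined protocol and SAP*

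**What the plan says.** Cohort 1 is 60 children aged 24 to 35 months. Section 3.1 states: "These children will be divided equally into two groups of 30, with one group receiving IIV and the other receiving LAIV as described above". Section 8.3, like section 2.1, gives the method: "These children will be block randomized to receive either LAIV (n=30) or IIV (n=30) in groups of 5 unless a history of isolated wheezing". The wheeze that counts is that of the preceding 12 months. For those children, "eligible children who give a history of isolated wheezing will be defaulted to receive IIV". Section 13.2 again describes 60 children in two groups of equal size, and section 13.1 rests the sample size on this: "recruiting n=30 subjects in each group will give us adequate power (0.815) for Aim 1".

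The defaulted children are part of the 60; no separate stratum or additional places are described. Section 2.2 expects such children and includes them to help recruitment, saying that "there is a large population of children with a past history of isolated wheezing as a result of viral illnesses such as bronchiolitis". It accepts that their inclusion rules out fully blinded randomisation, and says that they respond equivalently to influenza vaccine.

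The documents do not give the expected share of wheezing children, the allocation ratio for LAIV-eligible children, or what happens when one arm is full. Section 13.2 plans no analysis restricted to randomised children and no adjustment for wheeze or enrolment date.

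**The concern.** Two rules share one quota. Arm totals of 30 and 30 are natural when every child is randomised. Here some children enter IIV without randomisation and take places in it, so the eligible children make up the difference by going to LAIV more often than to IIV.

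This is separate from the wording about groups of 5. Concealed blocks of random size would leave it in place, because the cause is the quota combined with the default rule.

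What is at stake is the randomised basis of the Aim 1 comparison. In an open-label, single-centre study (sections 2.1 and 8.6), staff can see each default and each arm's count. Depending on the unstated fill rule, either a late run of eligible children goes to LAIV with no IIV children enrolled alongside, or the chance of LAIV shifts each time a wheezing child enters. The first mixes vaccine with enrolment time. Both make the next assignment easier to guess before consent.

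**Working it through.** **Inputs.** Total 60, arms 30 and 30 (sections 2.1, 3.1, 8.3, 13.2). Difference d = 0.3 and SD = 0.4 on the log10 scale, Student's two-sample t-test (section 13.1). Two-sided alpha of 0.05 is inferred: it reproduces the power table, and one-sided alpha does not (0.890 for 30 v 30). The number of defaulted children, k, is not in the documents. The shares used below, 5 to 30%, are assumptions.

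**Step 1: the plan's own figure.** Power comes from the noncentral t distribution with n1+n2-2 degrees of freedom and noncentrality (d/SD)/√(1/n1+1/n2). For 30 v 30 this is 0.75/√(2/30) = 2.905 on 58 degrees of freedom, giving 0.815. It matches, as do all 18 cells of the table.

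**Step 2: the forced split.** Eligible children number 60-k. LAIV needs 30 of them, leaving 30-k for IIV, so the average chance of LAIV for an eligible child is 30/(60-k).

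| k | LAIV : IIV among eligible | Chance of LAIV |
|---|---|---|
| 0 | 30:30 | 0.50 |
| 3 | 30:27 | 30/57 = 0.53 |
| 6 | 30:24 | 30/54 = 0.56 |
| 12 | 30:18 | 30/48 = 0.63 |
| 18 | 30:12 | 30/42 = 0.71 |

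**Step 3: what each fill rule would do.**

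- *1:1 blocks until IIV reaches 30, then LAIV only.* Simulated with permuted blocks of 2 to 10, wheezing children going to IIV and both arms capped at 30. The mean number of eligible children given LAIV by default at the end is about 3.3, 5.8, 10.3 and 14.0 at 5, 10, 20 and 30% wheeze. Divided by 30, that is 11, 19, 34 and 47% of the LAIV arm. Block size hardly matters. A LAIV tail occurs in 91 to 98% of runs at 5% wheeze, about 99% or more at 10%, and in every run at 20 and 30%. The tail roughly equals the number of wheezing children who got a place; at the higher shares this is below 60 times the share, because those arriving after IIV is full have no place.
- *Defaults use IIV places, or an unequal ratio is preset.* There is no certain tail. With a preset random order of 30 LAIV and 30-k IIV, the last eligible child gets LAIV with probability 30/(60-k), as in the table. With slot use, the chance of LAIV for the next eligible child rises after each visible default.

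**Step 4: what the quota buys in power** (d = 0.3, SD = 0.4).

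| k | All 60, quota dropped | Randomised only, quota dropped | Randomised only, quota kept |
|---|---|---|---|
| 6 | 27 v 33: 0.811 | 27 v 27: 0.772 | 30 v 24: 0.767 |
| 12 | 24 v 36: 0.799 | 24 v 24: 0.720 | 30 v 18: 0.692 |
| 18 | 21 v 39: 0.778 | 21 v 21: 0.660 | 30 v 12: 0.573 |

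Against 0.815 with the quota, the whole-cohort loss is 0.815-0.811 = 0.004 to 0.815-0.778 = 0.037. Among randomised children, dropping the quota raises power.

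**The case against.** The best defence is that the plan sets targets and not a procedure. Sections 2.1 and 8.3 speak of what is planned, section 3.1 of what is anticipated, and no section states a hard cap or says that wheezing children are turned away once IIV is full. A reader might infer that the last eligible children are certain to get LAIV, or that the totals can be met only by a late LAIV run or by slot use. The documents support neither inference. A certain tail needs 1:1 allocation run to a cap of 30; a concealed list with a preset unequal ratio also reaches 30 and 30 without one, though k would have to be foreseen; and the totals could simply drift. This part of the objection stands, so the tail is stated only as a conditional result.

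The size is also uncertain. Section 2.2 refers to any past isolated wheeze, whereas the default applies to the past year, and asthma needing controller medication is excluded. That sentence therefore does not establish a share, and at 5% the mean tail is only about 3 children. Nor do the documents say that late LAIV children would fall in a later season, since they give no enrolment calendar for cohort 1. The endpoint is a laboratory assay with a baseline sample, which limits the harm from predictable allocation without removing it.

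Section 2.2 does not answer the point. It concedes the loss of blinding and argues that wheezing children respond similarly. It does not address how eligible children are divided or when they are enrolled.

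**Conclusion.** The point holds as follows. With arms fixed at 30 and 30 and k defaulted children counted in IIV, eligible children must split 30:(30-k). This is arithmetic on the plan's own rules and needs no assumption beyond k being above zero, which section 2.2 expects. The chance of LAIV for eligible children then averages 0.53 to 0.71 for k from 3 to 18.

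A late LAIV-only run of about 3 to 14 children depends on two further assumptions: a wheeze share of 5 to 30%, and 1:1 allocation to a hard IIV cap. Neither is in the documents.

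A reader might also infer that the stated power of 0.815 is wrong. It is not, for a comparison of all 60 children at 30 v 30. What is weakened is the randomised basis of that comparison, since children with recent wheeze can appear only in IIV and eligible children are unevenly allocated. This is a worthwhile and cheap improvement to the design.

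**What to change.** In sections 2.1, 3.1, 8.3, 13.1 and 13.2:

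- Drop the fixed totals of 30 and 30 and keep 60 children.
- Allocate every LAIV-eligible child 1:1 from one concealed list until the 60th child is enrolled. Children whom the protocol already defaults to IIV use no list slot and count toward no arm cap.
- State the expected sizes as about (60-k)/2 LAIV and (60+k)/2 IIV.
- State Aim 1 power for all children (0.811, 0.799 and 0.778 at k = 6, 12 and 18) and for randomised children only (0.772, 0.720 and 0.660).
- Report the LAIV v IIV comparison in randomised children alongside the comparison in all children.
- Recompute the Aim 3 power, which section 13.1 bases on groups of 30, 30, 30 and 15, with the new cohort 1 sizes.

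The cost is wording and one list, with no extra children. The downsides are unequal arms, a smaller LAIV group (about 27 to 21 at 10 to 30% wheeze), and a stated whole-cohort power lower by about 0.004 to 0.037. A costlier alternative is to randomise 60 eligible children 30:30 and enrol wheezing children in addition. That keeps 0.815 for the randomised comparison, but needs about 60/(1-share) children: 67, 75 or 86 at 10, 20 or 30%.

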The second cohort of children will be infants between 3 and 12 months of age who will be enrolled to investigate how the primary CD4 T cell response that develops following IIV administration differs from that established after natural influenza infection. Infants who receive vaccine in this cohort will be at least 6 months of age and will be enrolled in the fall before influenza begins to circulate in the community. Infants between 3 and 12 months of age who contract a natural influenza infection before any doses of vaccine are administered will be eligible for the natural infection arm of this cohort. Both of these infant groups will have blood drawn and a nasal wash obtained on study entry and at days 10 (+ 4d/- 2d) and 24 (+/- 4d) post-vaccination and then will be followed to the subsequent influenza season and rechallenged with IIV, with blood draws and nasal washes again completed pre-vaccination and at days 10 (+ 4d/- 2d) and 24 (+/- 4d) post-vaccination (Figure 3). Children who test positive for influenza will be allowed treatment with oseltamivir as recommended by the CDC (73). To accomplish this, the rapid influenza test result will be provided to the child's pediatrician, who will then coordinate treatment of the child.

Figure 3

[figure not shown]

Figure 3: Experimental schematic to determine whether the method of initial priming differentially poises subjects to respond to future influenza encounters. Subjects that receive LAIV, IIV, or that are naturally infected with influenza will have CD4 T cell and antibody responses examined at enrollment and at days 10 and 24 post vaccination. Cohort 1 contains children approximately 24-36 months of age. Cohort 2A contains infants 6-12 months of age in their first influenza season, while cohort 2B contains infants 3-12 months of age. All enrolled subjects will be followed longitudinally for a year and then will be revaccinated with IIV. CD4 T cell responses, antibody response, and transcriptional profiles will be examined prior to revaccination and at days 10 and 24 post vaccination.

2.2: Rationale for Study Design:

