Infants between the ages of 6 months and 1 year of age receiving IIV before influenza reaches epidemic levels in the community will be eligible to enroll in the vaccination arm of cohort 2. These infants will not be randomized as they can only receive IIV. Two doses of IIV separated by 28 days will be administered to these children as they will be influenza-vaccine naïve. Infants between 3 and 12 months of age who are unvaccinated and present with influenza-like illness will be eligible to enroll in the infection arm of cohort 2.

8.4: Accountability of Investigational Supplies:

Some children will receive their first dose of influenza vaccine at the time of study enrollment in the office of their primary care physician. The clinic will be responsible for storing and maintaining these vaccines as recommended by the manufacturer. A supply of both vaccines will also be stored in a secure, limited-access, temperature monitored refrigerator at 2°C to 8°C in the VRU until needed. The temperature of the storage unit will be monitored throughout the duration of the study and documentation of proper storage will

be maintained. In the event of accidental deep-freezing or disruption of the cold chain, the vaccines will not be administered.

8.5: Subject Withdrawal of Study Drug

No medications will be chronically administered as part of this study.

8.6: Emergency Drug Disclosure:

Vaccine administration will not be blinded.

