10. RISK/BENEFIT ASSESSMENT

10.1: Potential Risks and Protection against Risks:

The risks and discomforts of this study include risks associated with the vaccine, risks associated with the study procedures (blood drawing, nasal wash and nasal swab), and possible loss of confidentiality.

While there are possible risks associated with administration of either LAIV or IIV (commonly including the development of a low grade fever or fussiness, the development a runny nose, headache, or sore throat from LAIV, or pain, redness, or swelling at the injection site from IIV), the administration of influenza vaccine to children is considered the standard of care. Thus, these risks are no greater than what would be experienced by children receiving the standard of care.

Blood draws may cause transient discomfort, which will be minimized using sucrose water in infants or distraction in older children. Bruising at the blood draw site also may occur, but can be prevented or

mitigated by applying direct pressure to the draw site for several minutes post blood draw. Development of infection is also possible, although unlikely, and will be prevented through the use of sterile technique (alcohol swabbing and the use of sterile equipment). The volume of blood per kg body weight being drawn is within a range considered safe. Nasal swabs are very safe and carry no significant risk in infants or children. Risks occasionally associated with nasal swabs include brief, minor irritation, and, rarely, transient bleeding. Nasal washes are also considered minimal risk, with the main risk being mild transient irritation, or, possibly transient bleeding. Long term side effects from any of these procedures are considered extremely unlikely.

Personal information on study subjects and their parents will also be collected to determine study eligibility and to account for possible confounding factors when performing data analysis. Research personnel will make every effort to keep this information confidential; however, a risk of participation is that the confidentiality of this information could be lost.

10.2: Potential Benefits to Subjects:

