$$y_{kit} = \alpha_k + \beta_k G(i) + \gamma_{kt} + \delta_{kit}. \quad (0.1)$$

Here y_{kit} represents the k th response variable measured from the i th subject at the t th time point; α_k is the overall mean value of y_{kit} ; $G(i)$ is a binary variable which equals 0 if the i th subject is vaccinated with LAIV and 1 otherwise; β_k is a linear coefficient that quantifies the magnitude of the group-effect; γ_{kt} is a random effect term that quantifies the time effects; and δ_{kit} represents independent measurement errors. Likelihood ratio test will be used to test $H_0: \beta_k = 0$ against $H_1: \beta_k \neq 0$. **Aim 2:** Two groups of infants will be recruited for this aim. The first group (n=30) will receive a prime-boost IIV series; the other group (n=15) consists of infants who are infected by influenza naturally. Multiple clinical endpoints will be recorded at 3 time points for both groups. We will apply two sample *t*-test (or Wilcoxon rank-sum test, if Shapiro-Wilks test rejects the assumption of normality) at each time point to detect significant group differences. In addition, we will apply a linear mixed effect model similar to Equation (1.1) to detect the overall group effect. The resulting *p*-values will be properly adjusted to control for FDR at a 0.05 level. **Aim 3:** All subjects (four subgroups; n=105) will be followed longitudinally for a year and then be revaccinated with IIV. CD4 T cell responses, antibody responses, and transcriptional profile (high-throughput RNA-seq) will be measured at three time points: prior to IIV re-vaccination, d10 and 24 days post re-vaccination. We will apply one-way ANOVA *F*-test (or Kruskal-Wallis test, if the normality assumption is rejected) to detect significant group differences at each time point. Post-hoc analysis based on Tukey's adjustment will be used to test for significant differences between groups. We will also apply a linear mixed effect model similar to Equation (1.1) to detect the overall group effect. For high-throughput transcriptional data, first we will apply suitable pre-processing techniques such as non-specific filtering (81), normalization (82) and batch-effect removing

(83). We then select differentially expressed genes at each time point by specialized procedures such as DEseq (84) and DEGseq (85). Benjamini-Hochberg procedure will be used to control FDR at a 0.05 level for all analyses.

13.3: Data and Safety Monitoring:

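### The Aim 2 comparison of infection with IIV is partly confounded with age: 3 to 5 month olds can enter only the infection arm, and no planned Aim 2 test or model includes age.

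*Combined protocol and SAP*

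**What the plan says.** Section 3.2 gives the two arms of cohort 2 different lower age limits. For the IIV arm it is "Between 6 and 12 months to participate in the vaccination arm of cohort 2 (cohort 2A"; for the infection arm it is "Between 3 and 12 months to participate in the natural infection arm of cohort 2 (cohort 2B". The difference is deliberate. Section 2.1 repeats that "Infants who receive vaccine in this cohort will be at least 6 months of age", and the contraindication exclusion in section 3.2 makes an exception for "infants between 3 and 5 months presenting with natural influenza infection whose only contraindication is their current age".

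Allocation does nothing to balance age. Section 8.3 says of the vaccine infants that "These infants will not be randomized as they can only receive IIV".

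The schedule adds a further difference. Section 2.2 says of the IIV infants that "we will only interrogate the immune response following the second vaccine dose", and the doses are 28 (+14) days apart. Under section 5.1, visits 2 and 3 fall on days 38 and 52 after the first dose for IIV infants, against days 10 and 24 after presentation for infected infants.

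For Aim 2, section 13.2 applies a t-test or rank-sum test "at each time point to detect significant group differences", plus a mixed model like the Aim 1 equation. The terms of that equation are an overall mean, group, time and error. Section 10.1 says that personal information is collected partly "to account for possible confounding factors when performing data analysis", without naming age or a method.

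**The concern.** Infants of 3 to 5 months can appear in one arm only, and nothing in the design or the written analysis balances or models age. If CD4 responses change with age during infancy, part of any observed difference between infection and IIV reflects age. Neither the per-visit tests nor the mixed model can separate the two.

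Hypothesis 2 in section 1.1 attributes the difference to the route of first exposure, so the interpretation of Aim 2 is at stake. An age effect could mask a real difference or exaggerate one, depending on its direction.

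**Working it through.** **Inputs from the documents.** Ages 3–12 months (infection) and 6–12 months (IIV), section 3.2. Arms of 15 and 30, SD 0.4 and difference 0.4 on the log10 scale, power 0.871, section 13.1. Second dose at least 28 days after the first, section 2.2.

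**Inputs assumed.** Ages uniform within each range. Log10 response rising linearly by 0.02 to 0.06 per month. The documents give neither an age distribution nor an age slope.

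**1. Reproduce the plan's power.** Noncentral t, two-sided 0.05, 43 degrees of freedom:
- Noncentrality = (0.4/0.4) / √(1/30 + 1/15) = 1/√0.1 = 3.162.
- Power = 0.871, as stated. The plan's figure is correct for an unconfounded contrast.

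**2. Age gap.**
- Mean age at entry: (6+12)/2 = 9.0 months for IIV and (3+12)/2 = 7.5 for infection, a gap of 1.5 months.
- At visit 2: 1.5 + 28/30.4 = about 2.4 months. A second dose given later than day 28 widens this.
- Expected share of infected infants under 6 months: (6−3)/(12−3) = 1/3, or 5 of 15.

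Visit 2 is the relevant time for the planned difference. For IIV infants the visit 1 sample is taken before vaccination, so the 0.4 difference does not apply to the entry comparison.

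**3. Bias and power at visit 2.** Bias = slope × 2.4 months. The infection arm is younger, so a rising response biases against infection.

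| Slope per month | Bias (log10) | Remaining difference | Noncentrality | Power |
|---|---|---|---|---|
| 0.02 | 0.048 | 0.352 | 2.783 | 0.78 |
| 0.06 | 0.144 | 0.256 | 2.024 | 0.51 |

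If the response falls with age at the same rates, the bias reverses sign and a true difference of 0.4 would be estimated as about 0.45 to 0.54.

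**4. False positives when infection has no effect.** At bias 0.048 the two-sided rate is 0.066. At bias 0.144 it is 0.20, of which 0.1985 is IIV appearing higher and 0.001 is infection appearing higher.

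**5. A different assumed shape.** Suppose instead that 5 of 15 infected infants are under 6 months and respond lower by 0.1 to 0.4 log10. The bias is 5/15 of that, 0.033 to 0.133, and simulated power is about 0.81 to 0.51. The order of size is similar, and it is equally dependent on assumption.

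**6. Power of the remedies at difference 0.4, SD 0.4.**
- Linear adjustment for age at enrolment, all 45 infants: mean variance inflation about 1.16 under uniform ages. Noncentrality 3.162/√1.16 = 2.94 on 42 degrees of freedom, power about 0.82.
- Linear adjustment for age at sampling: mean inflation about 1.36, power about 0.76.
- Infants of 6 months or more only, 30 v 10: noncentrality 1/√(1/30 + 1/10) = 2.739, power 0.761, which is also a cell of the plan's own table. With 3 or 8 of the 15 under 6 months, power is 0.815 (30 v 12) or 0.639 (30 v 7).

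The adjusted figures allow nothing for reduced residual variance.

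**The case against.** **The size is assumed.** This stands. Neither the age mix of the infection arm nor any age slope can be taken from the documents. The calculation also uses the sample-size variable, IFNγ-positive CD4 frequency, whereas hypothesis 2 concerns repertoire breadth and IL-2 producing cells. The figures illustrate scale and do not estimate bias in the hypothesis itself.

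**The arms overlap at 6 to 12 months.** This stands too: confounding is partial. The overlap is also what makes a remedy possible.

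**Adjustment is not ruled out.** Section 13.2 describes its strategies as an outline, its model only resembles the Aim 1 equation, and section 10.1 mentions confounding. A reader might infer that the plan commits the investigators to attributing every age effect to infection. The documents do not support that: adjustment is unspecified, not excluded. But a general sentence in the risk section, naming neither variable nor method, does not supply the missing analysis. Section 3.3 deals with confounding only through exclusions for immunosuppression and blood products, and the one planned sensitivity analysis (section 5.5) concerns undocumented infection.

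**A false advantage for infection.** A reader might take the 0.20 false-positive rate to mean that Aim 2 could wrongly favour infection one time in five. Under the assumed rise with age, nearly all of those errors favour IIV, so a finding in favour of infection would be conservative and the cost is lost power. A false infection advantage needs a response that falls with age, and the documents do not establish either direction.

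**Conclusion.** The structural point holds on the documents alone: unequal age limits, no randomisation, and no age term in any planned Aim 2 test or model. The contrast is partly confounded with age if the plan is followed as written.

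Its size and direction are unknown. Under uniform ages and a rise of 0.02 to 0.06 log10 per month, the visit 2 bias is 0.05 to 0.14 log10 against infection, with power of 0.78 to 0.51 in place of 0.871. A fall with age would inflate the infection effect. The stated 0.871 is not an error; it presumes a contrast free of this bias. The point should be dealt with before the data are examined, because the remedy is cheap and is more credible when pre-specified.

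**What to change.** In section 13.2, under Aim 2:

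1. Fit a linear model of log10 response on arm and age in months at enrolment, and add the same age term to the mixed model.
2. Pre-specify beside it a comparison limited to infants aged 6 to 12 months at enrolment in both arms. It can use either the t-test or the rank-sum test, so it also serves when normality is rejected.
3. State that the adjusted model extrapolates the age slope below 6 months, where the IIV arm has no infants, and report both results.

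Use age at enrolment rather than age at sampling. The two-dose schedule itself sets part of age at sampling, and adjusting for it costs more precision. The consequence should be stated: the roughly 0.9 month added by the schedule (28/30.4) stays in the contrast as part of the IIV regimen.

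The change is to wording; eligibility, visits and data collection are untouched. The price is power: about 0.82 for the adjusted model before any gain from lower residual variance, and about 0.761 for the restricted comparison if 10 of 15 infected infants are 6 months or older. Give both figures in section 13.1 with their assumptions.
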